#### **Establishing a Pseudo-Site for the Analyses**

Small sites (i.e., sites that have less than 2 patients for any of the treatment arms) will be identified and the following method will be used for combining the data. Data from all small sites will be combined to form a single site in order to obviate non-estimable situations (i.e., at least 2 observations are needed to estimate variance) in the evaluation of the performance of the device by site. Once combined, the pooled site will remain as such for all analyses for which a site interaction effect is determined. If the pooled smaller sites represent a single site that has more than twice as many patients as the largest single site, however less than 3 times as many patients, the small sites will be ranked by size and divided into 2 pooled assignments using an alternating sequence (ABABAB). If the pooled smaller sites represent a site that has more than three times as many patients as the largest single site, however less than 4 times as many patients, the small sites will be ranked by size and divided into 3 pooled assignments using an alternating sequence (ABCABCABC). This methodology will be applied, based on the initial pooling of the smaller sites.

#### **8.3.5. Evaluating the Effect of Different Control Devices**

The method to be applied for examining the effect of different control devices will facilitate the generation of adjusted estimates to contrast against the unadjusted estimates. The adjusted

estimates for the primary effectiveness and safety endpoints will introduce the effect of different control devices; the unadjusted estimates for the primary effectiveness and safety endpoints will only consider the randomized treatment assignment in the model. This sensitivity analysis will address the fundamental question relative to the effect of the different devices and is considered more informative than adding an interaction term into the model for analysis. To provide further insight into the results, the model will be run with the interaction term retained for treatment and different control devices.

To assess the effect of different control devices used in the control arm of the study, a random effects model will be used to calculate the overall estimate adjusted for each of the 2 device types (Trevor and Solitaire). The model that will be used to derive the estimates and the standard errors is presented in the SAP. From the solution for fixed effects, the exponentiation of the estimates and the standard error will provide adjusted confidence limits to assess the effect.

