### 6.2. Control Device

Currently there are two FDA-cleared stent retriever families with indications for treatment of acute ischemic stroke: the Stryker Neurovascular Trevo® family and the ev3 Neurovascular/Medtronic Solitaire™ family. The Trevo® family consists of the Trevo ProVue®

Retriever, Trevo® XP ProVue Retriever, and Trevo NXT™ ProVue Retriever. The Solitaire™ Revascularization Device family includes the following: Solitaire™ Platinum, Solitaire™ 2, Solitaire™ 4, and Solitaire™ X.

All Control Devices used must be used within their Indications for Use.

The proposed Envi™-SR indications for use match the Trevo® family of devices. Hence the time from stroke onset to usage (up to 24 hours) and imaging criteria are identical and the inclusion/exclusion criteria for the NV-001 study align with this indicated patient population.

The Solitaire™ Revascularization Device family has similar indications for use, however the indicated time from stroke onset to usage is up to 16 hours from onset or time last seen well (TLSW). Therefore, in the case of a subject randomized to the Control Device at 16 to 24 hours from onset or TLSW, only the Trevo® family will be permitted to be used.

The devices in Table 6.1 are currently cleared and may be used as the Control Device.

Table 6.1: Control Devices for ENVI RCT		
Family	Product	Size
Stryker Neurovascular Trevo®	Trevo ProVue® Retriever	4x20mm
	Trevo® XP ProVue Retriever	3x20mm
		4x20mm
		4x30mm
		6x25mm
ev3 Neurovascular/ Medtronic Solitaire™	Solitaire™ Platinum Revascularization Device	4x20mm
		4x40mm
		6x20mm
		6x24mm
		6x40mm
	Solitaire™ X Revascularization Device	4x20mm
		4x40mm
		6x20mm
		6x24mm
		6x40mm
	Solitaire™ 2 Revascularization Device	4x15mm
		4x20mm
		4x40mm
		6x20mm
		6x30mm

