### **8.3.6. Evaluating the Effect of Different Envi™-SR Device Sizes**

The method to be applied for examining the effect of different Envi-SR device sizes will facilitate the generation of adjusted estimates to contrast against the unadjusted estimates. The adjusted estimates for the primary effectiveness and safety endpoints will introduce the effect of different Envi-SR device sizes; the unadjusted estimates for the primary effectiveness and safety endpoints will only consider the randomized treatment assignment in the model. This sensitivity analysis will address the fundamental question relative to the effect of the different Envi-SR device sizes and is considered more informative than adding an interaction term into the model for analysis. To provide further insight into the results, the model will be run with the interaction term retained for treatment and device size.

To assess the effect of different Envi-SR device sizes used in the study, a random effects model will be used to calculate the overall estimate adjusted for each of the device sizes. The model that will be used to derive the estimates and the standard errors is presented in the SAP. From the solution for fixed effects, the exponentiation of the estimates and the standard error will provide adjusted confidence limits to assess the effect.

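### The treatment-by-control-device and treatment-by-Envi-SR-size interactions in 8.3.5 and 8.3.6 have no degrees of freedom, because each factor exists in only one arm

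*Combined protocol and SAP*

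**What the plan says.** Section 8.3.5 concerns the "different control devices used in the control arm of the study", with two levels, the Trevo and Solitaire families. It contrasts two sets of estimates for the primary effectiveness and safety endpoints. The unadjusted estimates "will only consider the randomized treatment assignment in the model". For the adjusted ones, "a random effects model will be used to calculate the overall estimate adjusted for each of the 2 device types", with the fixed-effect solution exponentiated. It then adds that "the model will be run with the interaction term retained for treatment and different control devices".

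Section 8.3.6 repeats this template for the nine Envi-SR sizes of Table 2.1 and ends with "the model will be run with the interaction term retained for treatment and device size".

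Neither section says what value a subject in the other arm takes, and neither plans a comparison within one arm. For the exact form, 8.3.5 says "The model that will be used to derive the estimates and the standard errors is presented in the SAP", and 8.3.6 says the same. That model text is not in the document reviewed.

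Section 6.2 adds a restriction on family. For a Control subject at 16 to 24 hours, "only the Trevo® family will be permitted to be used".

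**The concern.** The same template serves in 8.3.4 (site, region) and 8.3.7 (time last seen well). Those factors occur in both arms, so adjusting for them and testing their interaction with treatment makes sense. Carried over to 8.3.5 and 8.3.6, it meets factors nested in one arm. No Envi-SR subject has a control family, and, as 8.3.6 is worded, no Control subject has an Envi-SR size.

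The plan already guards against this kind of problem elsewhere: the pseudo-site rule in 8.3.4 pools small sites to avoid quantities that cannot be estimated. Sections 8.3.5 and 8.3.6 have no such safeguard.

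What is at stake is supportive evidence. The non-inferiority comparison sets Envi-SR against two device families combined, and 8.3.5 is the only analysis described in the protocol of whether family matters. If its interaction model is run as stated, the interaction does not exist, and the adjusted treatment estimate depends on a coding choice that nobody has specified.

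**Working it through.** **Inputs.** Two control families (6.2, 8.3.5). Nine Envi-SR sizes (Table 2.1). Control sizes (Table 6.1). Planning rates of 46% Control and 50.5% Envi-SR, and 135 per arm (synopsis and 8.2). Maximum ITT 448, so 224 per arm (8.2). The documents give no family split; Trevo shares of 50, 70 and 90% are assumed.

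**The plan's own figure.** No figure is stated for the 8.3.5 or 8.3.6 models. The target of 270, which sets the arm sizes, can be checked with one-sided 2.5% and 80% power (8.2 states these for the 426-subject case; assumed the same here):

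n per arm = (1.960 + 0.842)² × (0.46×0.54 + 0.505×0.495) / (0.125 + 0.045)² = 7.849 × 0.4984 / 0.0289 = 135.4, rounded up to 136, or 272 in total against 270. It reproduces within 2 subjects.

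**Estimability, control family.** Only three cells can hold subjects: Envi-SR, Trevo and Solitaire. With treatment and device as fixed factors,

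- mean(Envi-SR) = α + τE + δnone
- mean(Trevo) = α + τC + δT
- mean(Solitaire) = α + τC + δS

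Add any constant to τE and subtract it from δnone: all three means stay the same, so τE − τC is not identified. If Envi-SR subjects are instead given the Trevo code, the treatment coefficient becomes Envi-SR versus Trevo. Given the Solitaire code, it becomes Envi-SR versus Solitaire. An interaction adds columns but no cells.

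**Ranks over the cells that can be occupied.**

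| Factor | Cells | Treatment + factor | Treatment × factor | Interaction df | Adjusted treatment effect estimable |
|---|---|---|---|---|---|
| Control family | 3 | 3 | 3 | 0 | No |
| Envi-SR size | 10 | 10 | 10 | 0 | No |
| Region (8.3.4) | 4 | 3 | 4 | 1 | Yes |
| Time last seen well (8.3.7) | 4 | 3 | 4 | 1 | Yes |

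The evidence is the interaction df and the estimability check, not the gap between columns and rank. An intercept, a treatment indicator and two level indicators give four columns of rank 3 for a fully crossed factor as well.

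**Other readings of size.** Suppose control sizes are also coded. By labelled size the arms share only 3x20: there are 19 cells, both ranks are 19, and the interaction still has 0 df, though treatment becomes estimable through that one size. By diameter the arms share 3 and 4 mm: 6 cells, ranks 5 and 6, interaction 1 df.

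**Random device intercept.** Sampling variance of the pooled difference: 0.505×0.495/135 + 0.46×0.54/135 = 0.003692, so the half-width is 1.96 × √0.003692 = 11.9 points. Let σ be the between-device SD, with equal family shares. If Envi-SR is its own device level, the variance gains 1.5σ²; if it carries no device effect, 0.5σ². For assumed σ of 2, 5 and 10 points the half-widths are 12.8, 16.9 and 26.8 points, or 12.2, 13.8 and 18.3. The answer depends on a coding choice and on a variance informed by about 1 df.

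**What can be estimated.** 95% half-widths in points, for example Trevo versus Solitaire at a 50% share: 1.96 × √[0.46×0.54×(1/67.5 + 1/67.5)] = 16.8.

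| Per arm | Trevo share | Trevo vs Solitaire | Envi-SR vs Trevo | Envi-SR vs Solitaire | Pooled |
|---|---|---|---|---|---|
| 135 | 50% | 16.8 | 14.6 | 14.6 | 11.9 |
| 135 | 70% | 18.3 | 13.1 | 17.5 | 11.9 |
| 135 | 90% | 28.0 | 12.2 | 27.9 | 11.9 |
| 224 | 50% | 13.1 | 11.3 | 11.3 | 9.2 |
| 224 | 70% | 14.2 | 10.2 | 13.6 | 9.2 |
| 224 | 90% | 21.8 | 9.5 | 21.7 | 9.2 |

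**The case against.** The strongest reply is that the protocol does not give the model. It defers to the SAP, which could nest device within arm. The adjusted model it names is a random effects model, and that can be fitted. Both parts stand, so the finding concerns the protocol wording only. They do not rescue the interaction sentence, which names treatment crossed with a factor that one arm does not have.

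A reader might infer that nothing planned here can be estimated, or that the output would be uninterpretable. That goes too far. The three cell means are all estimable, and a three-level model without interaction gives Envi-SR versus each family. A reader might also infer that no coding of size allows an interaction. Coding both arms by diameter would give 1 df, although 8.3.6 speaks only of Envi-SR sizes.

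A third tempting inference is that the non-inferiority claim fails without this analysis. The documents do not support it. Both sections describe sensitivity analyses, no decision rule uses them, and Control is defined as an FDA-cleared device. The plan's poolability wording, in 6.10.1, concerns geography.

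Finally, the replacement contrasts have limits of their own. Family is chosen after randomisation, by an unblinded operator (3.6) and on anatomy (6.8.3). Adjusting for the 6-hour time stratum does not remove the Trevo-only window, which begins at 16 hours. Both limits stand and are carried into the fix.

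**Conclusion.** Wrong as written, within the protocol wording. The treatment-by-control-device and treatment-by-Envi-SR-size interactions have 0 df, and a treatment effect adjusted for either as a fixed factor is not identified. This follows from which cells can hold subjects, so no sample size or interim decision changes it. It rests on reading each factor as its section words it, confined to one arm.

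The random-intercept version can be fitted but is fragile. With an assumed between-device SD of 5 points, the half-width rises from 11.9 to 13.8 or 16.9 points, depending only on how Envi-SR is coded.

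The primary non-inferiority test is not affected. The data can speak to family differences, but weakly: every Trevo-versus-Solitaire half-width in the table exceeds the 12.5-point margin, including those at 224 per arm.

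**What to change.** Delete both interaction terms, and state in the protocol and the SAP how the other arm is coded in any adjusted model that remains.

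- **8.3.5:** report Envi-SR versus Trevo, Envi-SR versus Solitaire, and Trevo versus Solitaire within Control, as risk differences with 95% confidence intervals, adjusted for the stratification factors. Label them descriptive and non-randomised. Restrict the family contrasts to subjects treated within 16 hours, or repeat them there, because only Trevo is permitted from 16 to 24 hours.
- **8.3.6:** report outcomes by size group within the Envi-SR arm, adjusted for occlusion site.

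If the SAP already uses nested coding, align the protocol with it.

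The cost is wording: no extra subjects and no new data. The downside is the wide family contrasts shown above, which the text should say cannot by themselves establish that the families are poolable.

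Recording the intended control family for every subject before randomisation would make a treatment-by-intended-family term estimable. It is an optional design choice rather than part of this correction, because device choice follows anatomy (6.8.3) and baseline angiography may come after randomisation (6.8.2.5).

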### **8.3.6. Evaluating the Effect of Different Envi™-SR Device Sizes**

The method to be applied for examining the effect of different Envi-SR device sizes will facilitate the generation of adjusted estimates to contrast against the unadjusted estimates. The adjusted estimates for the primary effectiveness and safety endpoints will introduce the effect of different Envi-SR device sizes; the unadjusted estimates for the primary effectiveness and safety endpoints will only consider the randomized treatment assignment in the model. This sensitivity analysis will address the fundamental question relative to the effect of the different Envi-SR device sizes and is considered more informative than adding an interaction term into the model for analysis. To provide further insight into the results, the model will be run with the interaction term retained for treatment and device size.

To assess the effect of different Envi-SR device sizes used in the study, a random effects model will be used to calculate the overall estimate adjusted for each of the device sizes. The model that will be used to derive the estimates and the standard errors is presented in the SAP. From the solution for fixed effects, the exponentiation of the estimates and the standard error will provide adjusted confidence limits to assess the effect.

### **8.3.7. Evaluating the Effect of Time Last Seen Well (0-6 hours and >6 to 24 hours)**

The method to be applied for examining the effect of time last seen well (TLSW) will facilitate the generation of adjusted estimates to contrast against the unadjusted estimates. The adjusted estimates for the primary effectiveness and safety endpoints will introduce the effect of the time last seen well (0-6 hours and >6 to 24 hours); the unadjusted estimates for the primary effectiveness and safety endpoints will only consider the randomized treatment assignment in the model. This sensitivity analysis will address the fundamental question relative to the effect of the time last seen well (0-6 hours and >6 to 24 hours) and is considered more informative than adding an interaction term into the model for analysis. To provide further insight into the results, the model will be run with the interaction term retained for treatment and time last seen well (0-6 hours and >6 to 24 hours).

To assess the effect of the time last seen well (0-6 hours and >6 to 24 hours), a random effects model will be used to calculate the overall estimate adjusted for the discrete time segments. The model that will be used to derive the estimates and the standard errors is presented in the SAP. From the solution for fixed effects, the exponentiation of the estimates and the standard error will provide adjusted confidence limits to assess the effect.

### 8.3.8. Deviations from the statistical plan

Any departure or deviation from these planned statistical methodologies will be documented and discussed in the Statistical Analysis Plan that will include the statistical rationale for change.

## 9. Amendment to the Protocol

Only NeuroVasc Technologies is allowed to modify this protocol. The change will be in the form of a protocol revision or amendment. Any modification that potentially affects subjects' rights or safety must also be approved by the IRB/EC/REB and other regulatory agencies. In an emergency situation, where action is necessary to protect the life or physical wellbeing of the subject, a departure from the protocol for an individual subject may be allowed, and that departure will be for that subject only. In such circumstances, the investigator must notify the IRB/EC/REB and NeuroVasc Technologies and must describe the conditions necessitating the departure from the protocol and the outcome of the emergency intervention in a written report. NeuroVasc Technologies will determine whether the subject is to continue in the study or be considered a major protocol deviation.

## 10. Deviations from the Protocol

### 10.1. Protocol Deviation (Major)

A *major protocol deviation* is defined as an event that resulted in an increased risk to a subject or others; affected the right, safety or welfare of a subject; or affected the integrity of the study. Major Protocol deviations include, but are not limited to, the following list:

- Failure to obtain informed consent prior to patient enrollment
- Failure to treat subject per randomized treatment assignment
- Enrolled (i.e., consented) subject did not meet the inclusion/exclusion criteria
- Subject did not attend follow-up visit
- Source data permanently lost
- Introduction of additional therapy (including direct aspiration) prior to attempting revascularization with assigned treatment device for three passes.

### 10.2. Protocol Deviation (Minor)

Any other events that do not comply with the requirements of the protocol will be considered *Minor protocol deviations*.

Protocol deviations include, but are not limited to, the following list:

- Incorrect version of the informed consent form used.
- Follow-up visit was outside the required window.

All protocol deviations (major and minor) from the study protocol must be reported to the appointed NeuroVasc Technologies representative/ study monitor on a protocol deviation form, regardless of whether medically justifiable, pre-approved by NeuroVasc Technologies or taken to protect the subject in an emergency. In addition, the investigator is required to adhere to the IRB/EC/REB procedures for reporting protocol deviations.

Investigators must obtain prior approval from NeuroVasc Technologies before initiating deviations from the investigational protocol, except in situations where necessary to protect the life or physical well-being of a subject in an emergency situation, or situations beyond the investigator's control (such as subjects not attending scheduled follow-up visits, etc.). Approval

for deviations shall be documented in writing and maintained in the investigator and clinical study files. All deviations will be reported to NeuroVasc Technologies, regardless of medical justification, pre-approval by NeuroVasc Technologies, or emergency nature. Subject-specific protocol deviations will be reported using the protocol deviation form eCRF. Non-subject-specific protocol deviations (e.g. unauthorized use of the investigational device in the US outside the study, unauthorized use of the investigational device in the US by a physician who has not signed the investigator agreement, etc.) shall be notified in writing to NeuroVasc Technologies. FDA regulations (21 CFR 812.140 (a) (4)) require investigators to maintain accurate, complete and current records, including documentation showing the dates of and reasons for each deviation from the protocol. Per 21 CFR 812.46 (a), failure to comply with the investigational plan may result in termination of the investigator's participation in the study.

## 11. Device Accountability

NeuroVasc Technologies is responsible for the traceability of the study device (Envi™-SR) for this clinical investigation. NeuroVasc Technologies assumes responsibility for maintaining the following records:

- Quantity of the devices, the dates the devices are delivered to study sites.
- Lot numbers of all devices to be used for the study.
- Records of the shipment of the study devices and ancillary supplies to study sites.

NeuroVasc Technologies will ship devices only to qualified sites participating in the investigation which have the appropriate traceability and stock management controls in place (e.g., locked cabinet/storage space.) The appointed NeuroVasc Technologies representative/ study monitor will ensure the study site meets the record-keeping requirements for accountability and reconciliation of the study devices and ancillary supplies as part of the Site Initiation Visit. The investigator is responsible for proper storage of received devices and ancillary supplies at the hospital, and for maintaining a current device-tracking log for the duration of the study. The study monitor will review device storage conditions and the completion of the site's device tracking log. Reconciliation of device disposition will be documented. The names of all persons who received, used, or disposed of any device at the site will be recorded.

Records for the return of all study devices and ancillary supplies to NeuroVasc Technologies will be completed by the study site, verified by the appointed NeuroVasc Technologies representative /study monitor), and final disposition records will be maintained by NeuroVasc Technologies.

## 12. Safety and Adverse Events

### 12.1. Safety and Adverse Event Terms

An **Adverse Event (AE)** is any untoward medical occurrence, unintended disease or injury, or untoward clinical signs (including abnormal laboratory findings) in subjects, users or other persons, whether or not related to the investigational medical device.

An **Adverse Device Effect (ADE)** is any untoward and unintended response to a medical device. This includes Serious Adverse Device Effects and any event resulting from insufficiencies or inadequacies in the instructions for use or the deployment of the device, and any event resulting from a user error.

The term **All-cause Mortality** is utilized for death from any cause.

**Procedure-related Mortality** is utilized for death that occurs within a period of 7 days after the procedure or prior to discharge.

**Procedure Related Serious Adverse Events (PRSAE)** is where the interventional procedure caused, or cannot be ruled out as having caused, an effect that has resulted in any of the consequences characteristic of a serious adverse event.

A **Serious Adverse Event (SAE)** is an adverse event which:

1. Led to death,
2. Led to serious deterioration in the health of the subject, that either resulted in
  - a. A life-threatening illness or injury, or
  - b. A permanent impairment of a body structure or a body function, or
  - c. In-patient or prolonged hospitalization, or
  - d. Medical or surgical intervention to prevent life-threatening illness or injury or permanent impairment to a body structure or a body function.
3. Led to fetal distress, fetal death or a congenital abnormality or birth defect

NOTE: Planned hospitalization for a pre-existing condition, or a procedure required by the CIP, without serious deterioration in health, is not considered a serious adverse event.

A **Serious Adverse Device Effect (SADE)** is an Adverse Device Effect that has resulted in any of the consequences characteristic of a Serious Adverse Event (only device related).

**Unanticipated Adverse Device Effect (UADE)** means any serious adverse effect on health or safety or any life-threatening problem or death caused by, or associated with, a device, if that effect, problem, or death was not previously identified in nature, severity, or degree of incidence in the investigational plan or application (including a supplementary plan or application), or any other unanticipated serious problem associated with a device that relates to the rights, safety, or welfare of subjects.

**Unanticipated Serious Adverse Device Effect (USADE)** means any serious adverse device effect which by its nature, incidence, severity or outcome has not been identified in the current version of the risk analysis report.

